6.4.2. Subjects Randomized to Epoetin Alfa

Subjects randomized to epoetin alfa will be administered according to local labelling and clinical practice guidelines to keep Hgb in the target range (10.0-11.0 g/dL). For additional guidance on Hgb-based stopping criteria please refer to Section 5.5.1.1.

6.5. Packaging and Labeling

Daprodustat tablets are packed in white, opaque high density polyethylene (HDPE) bottles with child-resistant closures. The contents of the label will be in accordance with all applicable regulatory requirements.

6.6. Preparation/Handling/Storage/Accountability

No special preparation of study treatment is required.

- Only subjects enrolled in the study may receive study treatment and only authorized site staff may supply or administer study treatment. All study treatments must be stored in a secure environmentally controlled and monitored (manual or automated) area in accordance with the labelled storage conditions with access limited to the investigator and authorized site staff.
- The investigator, institution, or the head of the medical institution (where applicable) is responsible for study treatment accountability, reconciliation, and record maintenance (i.e., receipt, reconciliation and final disposition records).
- Further guidance and information for final disposition of unused study treatment are provided in the Study Reference Manual (SRM).

- Under normal conditions of handling and administration, study treatment is not expected to pose significant safety risks to site staff.
- A Material Safety Data Sheet (MSDS)/equivalent document describing occupational hazards and recommended handling precautions either will be provided to the investigator, where this is required by local laws, or is available upon request from GSK.

6.7. Compliance with Study Treatment Administration

For subjects randomized to daprodustat, treatment dosing details including dates for dose increases/reductions, will be recorded in RAMOS NG.

For subjects randomized to daprodustat, for Acute Challenge 1 and 2, study site personnel will confirm compliance. When daprodustat is administered at home (Hgb maintenance period), subjects will be instructed to return all unused randomized treatment at each clinic visit. A record of the number of daprodustat tablets dispensed to and taken by each subject will be maintained and reconciled with randomized treatment and compliance records.

For subjects randomized to epoetin alfa, they will receive all study treatment directly from the investigator or designee, under medical supervision. The date and time of each dose administered in the clinic will be recorded in the source documents. The dose of study treatment and study subject identification will be confirmed at the time of dosing by a member of the study site staff other than the person administering the study treatment.

6.8. Treatment of Study Treatment Overdose

There is no specific antidote for overdose with daprodustat. The expected manifestations of daprodustat overdosage include signs and symptoms associated with an excessive and/or rapid increase in Hgb concentration. Daprodustat is highly protein bound; thus, clearance of daprodustat by HD is very low and this is not an effective method to enhance the elimination of daprodustat. Daprodustat metabolites are, in part, cleared via hemodialysis. In the event of a suspected overdose, it is recommended that the appropriate supportive clinical care be instituted, as dictated by the subject's clinical status. Additionally, subjects should be monitored closely for CV events, increased heart rate and hematologic abnormalities.

Consult the approved product label for information on overdose for epoetin alfa.

6.9. Treatment after the End of the Study

Subjects will not receive any additional treatment from GSK after completion of the study because the indication being studied is not life threatening or seriously debilitating and other treatment options are available.

The investigator is responsible for ensuring that consideration has been given to the post-study care of the subject's medical condition.

6.10. Lifestyle and/or Dietary Restrictions

6.10.1. Meals and Dietary Restrictions

Daprodustat can be taken without regard to meals.

All subjects will be instructed to limit caffeine- or xanthine- containing products (e.g., coffee, tea, cola drinks, chocolate) for 24h prior to both Acute Challenge 1 and Acute Challenge 2.

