4. STUDY DESIGN

4.1. Overall Design

This study will be an open-label, randomized, parallel-group design in HD subjects with anemia associated with CKD. There will be a screening period, a 2-week ESA washout

period, an initial 24-hr Acute Challenge, an 8-week Hgb-maintenance period, a second 24-hr Acute Challenge and a follow-up visit 14±3 days after completing treatment. The study design is outlined in [Figure 1](#).

Figure 1 Study Design

Subjects will be screened for eligibility within 7-30 days prior to the start of an ESA washout period.

Subjects that qualify for enrolment will be washed out of their ESA for 2 weeks; the start of the ESA washout should be timed to coincide as closely as possible with their next planned ESA dose. Subjects are enrolled once they enter the ESA washout period.

Following the 2-week ESA washout, subjects will be randomized 1:1 and stratified by prior ESA dose, based on the average weekly (for epoetins or darbepoetin) or monthly (for methoxy polyethylene glycol (PEG)-epoetin beta) dosing during the 12 weeks prior to ESA washout as follows:

- Low ESA dose: <100 U/kg/week epoetin alfa OR <0.5 µg/kg/week darbepoetin OR <0.6 µg/kg/week methoxy PEG-epoetin beta
- High ESA dose: ≥100 U/kg/week epoetin alfa OR ≥0.5 µg/kg/week darbepoetin OR ≥0.6 µg/kg/week methoxy PEG-epoetin beta

On Day 1, subjects will be randomized and undergo Acute Challenge 1, a single dose challenge to compare the acute effects on BP of the highest planned once-daily maintenance dose of daprodustat (24 mg) to the highest starting dose of epoetin alfa (100 U/kg). Subjects will have BP monitored for 24 hr using ABPM, and will have serial blood sampling to assess the pharmacokinetics of daprodustat and the time-course of various biomarkers. Acute Challenge 1 will be started promptly following completion of a mid-week dialysis session.

After completing Acute Challenge 1, all subjects will enter the 8-week Hgb maintenance period where doses of either daprodustat or epoetin alfa will be administered and adjusted, as needed, based on dosing guidance as described in [Section 6.4](#).

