4.2. Treatment Arms and Duration

The total duration of subject involvement is up to 16 weeks (Screening to Follow-up) as described below:

- Screening: Screening will occur at least one week prior to but not more than 30 days prior to washout.
- ESA Washout: Subjects that meet eligibility criteria will begin the 2-week ESA washout at Week -2.
 - This should be timed such that this day occurs on the date that would have been the next scheduled dose of ESA (or as close as practicable).
 - For subjects with a three-times weekly dialysis schedule, this day must not occur on the first dialysis session of the week (e.g., if Monday-Wednesday-Friday schedule, the study visit cannot be on Monday).
 - For subjects with a four- to five-times weekly dialysis schedule, this day can be on any hemodialysis session of the week.
- Randomization & Acute Challenge 1 (Day 1): Subjects will be randomized 1:1 to two treatment arms as described in [Table 1](#) and will begin a 24-hr Acute Challenge where the acute BP effects of daprodustat and epoetin alfa will be

evaluated. This challenge will be initiated promptly following the subject's dialysis session.

- **Hgb Maintenance Period:** Subjects randomized to daprodustat will start an 8-week Hgb maintenance period based on a starting dose and dose adjustment algorithm as described in Section 6.4.1. Subjects randomized to epoetin alfa will begin an 8-week Hgb maintenance period where Hgb will be managed in accordance with local labelling.
- **Acute Challenge 2:** At the end of the 8-week Hgb maintenance period, subjects will repeat the procedures of Acute Challenge 1 utilizing the same treatment administered in Acute Challenge 1. This challenge will be initiated promptly following the subject's dialysis session.
- **Follow-up:** A Follow-up visit will be scheduled to occur 14 ± 3 days after completing treatment.

Table 1 Treatment Arm Descriptions

Treatment Arm	Acute Challenge 1	Hgb Maintenance Phase	Acute Challenge 2
A	100 U/kg IV epoetin alfa	IV epoetin alfa according to label	100 U/kg IV epoetin alfa
B	24 mg daprodustat	QD daprodustat according to dose adjustment algorithm (Section 6.4.1)	24 mg daprodustat

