7.5. Biomarker(s)/Pharmacodynamic Markers

7.5.1. Ambulatory Blood Pressure Monitoring (ABPM)

Blood pressure and pulse will be measured during Acute Challenge 1 and 2 through the use of an ambulatory blood pressure monitoring device. Subjects will wear the ABPM device for two sessions during the study (i.e., Acute Challenge 1 and 2), occurring at Day 1 (randomization) and at Day 57. The ABPM device will be placed prior to Acute Challenge dosing, and will remain on the subject's arm until 24 hrs post-dosing.

ABPM measurements of systolic and diastolic blood pressure and heart rate will be automatically recorded every 15 minutes for the first 6 hrs post-dosing, and then every 20 minutes thereafter until 24 hrs post-dosing. The ABPM device will automatically calculate MAP.

The device planned for use in this study is the Mortara Ambulo 2400; a specification sheet for this device can be found in Section [12.6](#).

After both Acute Challenge 1 and 2, the 24-hr ABPM results will be checked for data quality as defined in the Project Requirement Specification (PRS). If the ABPM fails the QC criteria following Acute Challenge 2, one additional Acute Challenge may be made in a subsequent, mid-week dialysis visit 1 week later if the subject agrees. At that visit, the subject will receive the same study treatment for the repeat Acute Challenge 2 as was administered on Day 57 as a single additional dose. No additional clinical chemistry, hematology, pharmacokinetic or biomarker sampling will be done, however all other procedures will be performed as detailed in [Table 4](#).

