9. STATISTICAL CONSIDERATIONS AND DATA ANALYSES

The primary endpoint for this study is average systolic blood pressure (SBP) over 6 hours of measurements taken at 15-minute intervals after the administration of study treatment for the Acute Challenge 2. The primary comparison of interest is daprodustat versus epoetin alfa for this challenge.

The comparison of daprodustat versus epoetin alfa on 6 hr average SBP during Acute Challenge 1 is a secondary endpoint.

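### The caffeine and xanthine limit covers only the 24 h before each Acute Challenge, so it lapses at about dosing and leaves the 6-h primary window uncovered; the cost is modest noise and the remedy is cheap.

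*Protocol*

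**What the plan says.** Protocol Section 6.10.1 is the only current text on caffeine or xanthines. "All subjects will be instructed to limit caffeine- or xanthine- containing products", and the period given is "for 24h prior to both Acute Challenge 1 and Acute Challenge 2". The word is limit, not abstain, and no amount is set. The section gives no reason for the limit.

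Sections 4.1 and 4.2 define what the limit precedes. Subjects "undergo Acute Challenge 1, a single dose challenge to compare the acute effects on BP"; under Section 4.2 they "will begin a 24-hr Acute Challenge where the acute BP effects of daprodustat and epoetin alfa will be" evaluated, and "This challenge will be initiated promptly following the subject's dialysis session". Section 7.5.1 adds: "The ABPM device will be placed prior to Acute Challenge dosing, and will remain on the subject's arm until 24 hrs post-dosing". Blood pressure is "automatically recorded every 15 minutes for the first 6 hrs post-dosing" and every 20 minutes after that.

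The primary endpoint in Section 9 is "average systolic blood pressure (SBP) over 6 hours of measurements taken at 15-minute intervals after the administration of study treatment" in Acute Challenge 2. The secondary area-under-the-effect-curve endpoints use the full 24 h.

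Other places where the limit might have been extended do not mention it: the challenge-day schedule (Section 7.1, Table 4), the ambulatory monitoring section (7.5.1), the SAP covariates (5.4.1) and the SAP per-protocol exclusions (14.1.1).

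**The concern.** A limit on caffeine around a blood pressure challenge is most useful while blood pressure is being measured. As written, it covers the run-up and stops as the measurement begins. A subject who has cut down for a day and has just finished dialysis may take coffee, tea or cola during the 6 h that make up the primary endpoint without departing from the protocol.

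The baseline covariate does not help. Under SAP Section 14.6.6 it is the first ambulatory reading or, failing that, the post-dialysis vital sign. A response to something drunk after dosing enters the 6-h mean but not that reading, so the ANCOVA cannot adjust for it. Two things are at stake: some avoidable residual variance in the primary comparison, and some distortion of the change-from-pre-dose profiles shown for each arm.

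**Working it through.** **1. Timing.** Four pieces of text, in time order:

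| Period | Source | Caffeine limit in force? |
|---|---|---|
| 24 h before the challenge | Protocol 6.10.1 | Yes |
| Pre-dose baseline reading | Protocol 7.5.1, SAP 14.6.6 | At the end of the limited period |
| 0-6 h after dosing (primary endpoint) | Protocol 9 | None stated |
| 6-24 h after dosing (rest of the recording) | Protocol 7.5.1 | None stated |

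That the limit ends at dosing is an inference from the words prior to, together with the definition of the challenge as a single dose followed by 24 h of recording. Any gap between the end of dialysis and the dose should be short, because the challenge starts promptly after the session.

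**2. The plan's own figures.** Protocol 9.2.1 assumes SD 16 mmHg, 25 subjects per arm, a 15 mmHg difference and a 5% significance level; the confidence interval in 9.4.1 is two-sided. With a two-sample t test on 48 degrees of freedom:

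- half-width = t(0.975, 48) × SD × √(2/n) = 2.011 × 16 × √(2/25) = 9.10 mmHg;
- power from the noncentral t = 90.1%.

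Both agree with Table 6 (9.1 mmHg and 90%).

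**3. Added noise.** The documents give neither a caffeine effect nor an intake rate, so both are assumed. Let a proportion p of subjects in each arm take caffeine in the window, and let it shift their 6-h mean by e mmHg. The added between-subject variance is p(1 − p)e², and the total SD is √(256 + p(1 − p)e²).

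| p | e (mmHg) | Added SD | Total SD | Power | Half-width (mmHg) |
|---|---|---|---|---|---|
| 0 | – | 0 | 16.00 | 90.1% | 9.10 |
| 0.3 | 2 | 0.92 | 16.03 | 90.0% | 9.11 |
| 0.3 | 5 | 2.29 | 16.16 | 89.5% | 9.19 |
| 0.3 | 8 | 3.67 | 16.41 | 88.6% | 9.33 |
| 0.5 | 2 | 1.00 | 16.03 | 90.0% | 9.12 |
| 0.5 | 5 | 2.50 | 16.19 | 89.4% | 9.21 |
| 0.5 | 8 | 4.00 | 16.49 | 88.3% | 9.38 |

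The worst case costs 90.1 − 88.3 = 1.8 points of power and 9.38 − 9.10 = 0.28 mmHg of half-width.

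**4. Bias, only if intake differs by arm.** Bias = (difference in intake) × e. With equal intake it is zero. For a hypothetical 20-point difference it is 0.2 × 2 = 0.4 mmHg up to 0.2 × 8 = 1.6 mmHg, in either direction. If it shrank a true 15 mmHg effect, power would be 88.5% to 82.7%. If the true difference were zero, the two-sided type I error would be 5.1% to 6.4%. Nothing in the documents points to such a difference.

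**The case against.** The strongest reply is that the effect is small, and that stands. The worst case in the table gives SD 16.5, while Protocol Table 7 already examines SDs of 18 and 20. Adding variance to 16 may also double count: Section 9.2.1 calls 16 mmHg the true SD of the 6-h average and does not say that it excludes what subjects ordinarily drink. If it includes ordinary intake, the plan loses no power against its stated figure and only forgoes a small gain.

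A reader might infer that the primary treatment contrast is biased, because the trial is open-label and the Time and Events tables do not list caffeine intake. The documents do not support that. Allocation is randomised 1:1, both arms follow essentially the same challenge-day schedule, and no reason appears for coffee drinking to differ by arm. A shift common to both arms cancels in expectation in the between-arm difference. Open-label conduct leaves unequal intake possible, but not expected. For the same reason, a caffeine response could pass for a drug effect only in the within-arm displays.

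A reader might also infer that subjects are wholly unsupervised. Table 4 schedules blood draws and adverse event checks at 0.5, 1, 2, 3, 4 and 6 h, so many are probably under observation for much of the window. The protocol does not say that drinks are controlled then, however. The Study Reference Manual could carry a further instruction; it is not available here, and Section 6.10.1 does not refer to it.

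Lastly, since Section 6.10.1 gives no rationale, protecting the blood pressure measurement is an inferred purpose, though a natural one.

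**Conclusion.** The gap is in the text: the stated limit stops at about dosing, and nothing in the protocol or SAP carries it into the 6-h primary window or the 24-h recording. The consequence is modest. With assumed intake of 30-50% and assumed shifts of 2-8 mmHg, the added SD is 0.9-4.0 mmHg and the loss of power is at most about 2 points from 90%, or less if the planning SD already reflects ordinary intake. The change-from-pre-dose profiles within each arm are also exposed. Between-arm bias would require unequal intake and is not expected under randomisation. The point is a cheap improvement of minor severity, not a threat to the primary conclusion.

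**What to change.** Reword Section 6.10.1 so that the existing limit runs from 24 h before dosing until at least 6 h after dosing, and preferably until the 24-h ambulatory recording ends. Apply it at Acute Challenge 1, Acute Challenge 2 and any repeat Acute Challenge 2. The repeat should be named because Section 6.10.1 lists only the two scheduled challenges, while SAP Section 11.1.4 lets the repeat recording replace a failed one.

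The cost is one sentence in the protocol and in the subject instructions, plus 6 to 24 more hours of a limit already in place, on two or three occasions. If adopted during recruitment, it needs ethics review as an amendment and changes challenge-day conditions partway through. Some subjects would then have their two challenges under different rules. That change applies equally to both arms, so it should not bias the comparison. If the Study Reference Manual already extends the limit, a cross-reference in Section 6.10.1 is enough.

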6.11. Concomitant Medications and Non-Drug Therapies

Concomitant medications, including over-the-counter medications and supplements, taken during the study will be recorded in the eCRF. Start/stop dates and route of administration will be recorded for general concomitant medications.

6.11.1. Weight and Antihypertensive Medication Changes

It is preferred that changes to subject weight and antihypertensive medication(s) are not made while the subject is part of this study, however, subjects should remain in the study regardless of any changes. All medication and dose changes should be recorded in the eCRF.

6.11.2. Permitted Medications and Non-Drug Therapies

Unless specified as a prohibited medication in Section 6.11.3, all concomitant medications should be considered permitted provided they are not contraindicated for the individual subject concerned.

6.11.3. Prohibited Medications and Non-Drug Therapies

Use of any of the following prescription drugs from Screening until 7 days after the last dose of randomized treatment is prohibited and will constitute a protocol violation.

- Strong inhibitors of CYP2C8 (e.g., gemfibrozil, high dose clopidogrel [300 mg])
- Strong inducers of CYP2C8 (e.g., rifampin/rifampicin)

6.11.4. Standard of Care

During the study, investigators are expected to monitor the subject's overall clinical status to ensure standards of care are met to enable consistency of practice with Kidney Disease Improving Global Outcomes (KDIGO) guidelines or local equivalent.

6.11.5. Iron Protocol

Subjects must remain iron replete throughout the study. If ferritin and TSAT are collected per local clinical practice while enrolled, the following is recommended.

Iron therapy will be administered if ferritin is ≤ 100 ng/mL and/or TSAT is $\leq 20\%$. The investigator should choose the route of administration and dose of iron based on subject's iron status and local clinical practice.

All iron (excluding multivitamins) must be stopped and cannot be administered if:

- Ferritin > 800 ng/mL **AND** TSAT $> 20\%$ **OR**

- TSAT >40%

7. STUDY ASSESSMENTS AND PROCEDURES

Protocol waivers or exemptions are not allowed with the exception of immediate safety concerns. Therefore, adherence to the study design requirements, including those specified in the Time and Events Table (Section 7.1), are essential and required for study conduct.

- If assessments are scheduled for the same nominal time, then the assessments should occur in the following order:
 1. 12-lead ECG
 2. vital signs
 3. blood draws

Note: The timing of the assessments should allow the blood draw to occur at the exact nominal time.

- The change in timing or addition of time points for any planned study assessments must be documented in a Note to File which is approved by the relevant GSK study team member and then archived in the study sponsor and site study files, but this will not constitute a protocol amendment.
- The Institutional Review Board (IRB)/ Independent Ethics Committee (IEC) will be informed of any safety issues that require alteration of the safety monitoring scheme or amendment of the Informed Consent Form.
- No more than 550 mL of blood will be collected over the duration of the study, including any extra assessments that may be required.

Supplementary study conduct information is provided in the SRM. The SRM provides administrative and detailed technical information that does not impact subject safety.

7.1. Time and Events Table
Table 3 Study Procedures and Assessments

Procedure ¹	Screening	Washout	Treatment Period ²					Follow-up ²	
			Day 1	Day 15	Day 29	Day 43	Day 57	Early WD	Week 10
Informed Consent	X								
Entry Criteria	X								
Physical, Medical History, Demography	X								
HemoCue Hgb	X	X	X ⁴	X	X	X	X ⁴	X	X
Enrolment		X							
IVWRS			X	X	X	X			
Randomization			X						
Acute Challenge			X ⁴				X ⁴		
ABPM Assessment			X ⁴				X ⁴		
Dose Adjustment				X	X	X			
Females Only: Serum Pregnancy Test	X		X		X		X		X
Females Only: Estradiol & FSH (if required) ³	X								
ECG	X		X ⁴				X ⁴		X
Vital signs & weight (Pre- & Post-dialysis)	X	X	X ⁴		X		X ⁴		X
Clinical Chemistry	X		X		X		X		X
Hematology	X		X		X		X		X
Folate and Vitamin B12	X								
Ferritin, transferrin, total iron, TSAT, UIBC	X								
Pharmacokinetic/Biomarker Assessments			X ⁴				X ⁴		
Hgb Maintenance Period ⁵			←-----→						
Adverse Events Assessment	X ⁶	X	X ⁴	X	X	X	X ⁴		X
Review Concomitant Medications	X	X	X ⁴	X	X	X	X ⁴		X

1 All assessments should be done predialysis/predose except as noted.

2 Allowable time window ± 2 days EXCEPT Follow-up Visit which is ± 3 days.

3 As detailed in Inclusion Criteria.

4 Detailed timings for assessments on Acute Challenge Days are given in [Table 4](#).

5 From the end of Acute Challenge 1 to the beginning of Acute Challenge 2.

6 Only SAEs assessed as related to study participation are collected at this visit. See Section [12.4](#) for additional details.

Table 4 Study Procedures and Assessments on Acute Challenge Days (Treatment Period Day 1 and Day 57)

Procedure	Pre-Dialysis	Post-Dialysis	Predose	Time (in hours relative to dosing)										
				0	0.5	1	2	3	4	6	8	12	16	24
HemoCue Hgb ¹			X											X
IVWRS			X											
ABPM Assessment ^{1,3}			←=====→											
Administer Study Treatment ¹				X										
Serum Pregnancy Test ¹			X											
ECG ¹			X											X
Vital Signs and Weight ¹	X	X						X				X		X
Clinical Chemistry			X											
Hematology			X											
Pharmacokinetics ⁴			X		X	X	X	X	X	X	X	X	X	X
Erythropoietin			X		X	X	X	X	X	X	X	X	X	X
Endothelin-1			X		X	X		X	X	X				X
Nitric Oxide			X		X	X		X	X	X				X
Asymmetric dimethylarginine			X		X	X		X	X	X				X
Renin			X		X	X		X	X	X				X
Angiotensin-II			X		X	X		X	X	X				X
Noradrenalin			X		X	X		X	X	X				X
Adverse Events Assessment ¹			X		X	X	X	X	X	X	X	X	X	X
Review Concomitant Medications ¹			X											X
Initiate Hgb maintenance dosing ²														X

1 Procedures to be repeated if Acute Challenge 2 fails quality control criteria (For more detail refer to Section 7.5.1)

2 Applies to Acute Challenge 1 only

3 Timing of ABPM measurements does not correlate with specified time points in Table 4.

4 PK to be drawn from daprodustat subjects only.

